10.1.3 Analysis of Time-to-Event Data

Time-to-endpoints will be summarized by OAC with the number and percentage of patients with event, and event rates. Event rates will be calculated as the number of patients with event per 100 patient-years at risk. In addition, total patient-years will be presented for each OAC.

Patients who experience a clinical endpoint event after the earlier of their discontinuation of the index OAC, switching from the index OAC, withdrawal from the database, or the end of intended follow-up period (i.e., two years after the index date as primary and one year for a sensitive analysis) will be censored.

Patients who do not experience a clinical endpoint event will be censored at the earlier of their discontinuation of the index OAC, switching from the index OAC or withdrawal from the database will be censored.

Propensity score matching

See above

Cox proportional hazards model

Cox proportional hazards model will be used to compare endpoints in each of the propensity-score-matched cohorts, with robust sandwich estimates to account for the clustering within matched sets. The Cox proportional hazards model will include only index OAC treatment as the independent variable if patient characteristics are balanced between groups based on standardized difference in components of the PS. If not balanced, the unbalanced variable will be also included to the model in addition to the index OAC treatment. The hazard ratios with corresponding 95% confidence intervals and p-values will be reported.

CCI

Kaplan-Meier Method

For each endpoint, Kaplan-Meier curves will be plotted for the time from the index date to first event by index OAC treatment in each of the propensity-score-matched cohorts. The log-rank test is used for comparison between two curves.

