4.1 DATA SOURCE

The analysis will be based on administrative data from MDV Co. Ltd., a longitudinal database based on health insurance claims and medical records obtained from the hospitals in which the DPC payment system for utilization of both inpatient and outpatient hospital claims (percentage of inpatients is about 45%). The database provides claims data from 314 hospitals (as of June 2017) using the DPC system for medical service claims (21% of general hospitals but 55% of general beds in Japan is under the DPC system) including approximately 14 million patient data.

Treatment/cohort labels

- Apixaban Cohort: NVAF patients who initiated apixaban on the index date.
- Dabigatran cohort: NVAF patients who initiated dabigatran on the index date.
- Edoxaban Cohort: NVAF patients who initiated edoxaban on the index date.
- Rivaroxaban Cohort: NVAF patients who initiated rivaroxaban on the index date.
- Warfarin Cohort: NVAF patients who initiated warfarin on the index date

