6.2 STATISTICAL DECISION RULES

All statistical tests will be performed at $p=0.05$ (two-sided) with no adjustment for multiplicity.

Based on results of Japanese sub-population in confirmatory trials for NOACs, the required sample size to detect a significant difference in stroke/SE was calculated. The following sample size calculation is based on the significance level of 0.05 (two-sided) and power of 80%.

Desired Power	Hazard Ratio	Event Rate (Control)	Required Sample Size per Group
0.8	0.6	1.2 %/year	3,166
		1.6 %/year	2,378
		2.1 %/year	1,815
		2.6 %/year	1,469

Desired Power	Hazard Ratio	Event Rate (Control)	Required Sample Size per Group
	0.7	1.2 %/year	6,083
		1.6 %/year	4,570
		2.1 %/year	3,488
		2.6 %/year	2,823
	0.8	1.2 %/year	14,683
		1.6 %/year	11,031
		2.1 %/year	8,422
		2.6 %/year	6,817

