8.4 COVARIATES

We will use demographic and clinical information available at the index date and baseline period of the initiation prescription for apixaban, edoxaban, and warfarin cohorts.

Variable	Role	Operational definition
Sex Category	Baseline characteristic	Dichotomous variable equals 1 if sex is male and 2 if female
Age	Baseline characteristic	Age (in years) at the index date
Physician specialty	Baseline characteristic	Dichotomous variable equals 1 if a physician specialty on the index date is categorized into a cardiac specialty and 0 if others. Following specialties will be categorized as the cardiac specialty: cardiology stroke, cardiovascular surgery, pediatric cardiology, neurosurgery, cardiovascular medicine, and neurology. If there are ≥ 1 specialties but including the cardiac specialty, the physician specialty will be regarded as the cardiac specialty.
Hospital size (<500 beds or not)	Baseline characteristic	Dichotomous variable equals 1 if hospital size on the index date is <500 beds and 0 if ≥ 500 beds.
Hospitalization status on index date	Baseline characteristic	Dichotomous variable equals 1 if hospitalization status is inpatient and 0 if outpatient.
CHADS ₂	Baseline characteristic	CHADS ₂ score will be calculated based on age and the presence of congestive heart failure, hypertension, diabetes, and stroke or TIA.

CHA ₂ DS ₂ -VASC	Baseline characteristic	CHA ₂ DS ₂ -VASC score will be calculated based on age and the presence of congestive heart failure, hypertension, diabetes, stroke or TIA, vascular disease and sex category.
PT-INR (Prothrombin time-international normalized ratio)	Baseline period	Continuous variable. * Only available for patients treated with warfarin
Heart failure diagnosis in baseline	Baseline characteristic	Dichotomous variable equals 1 if there are ≥ 1 diagnoses for heart failure ICD-10 or disease codes during the baseline period.
Coronary heart disease diagnosis in baseline	Baseline characteristic	Dichotomous variable equals 1 if there are ≥ 1 diagnoses for coronary heart disease ICD-10 or disease codes during the baseline period.
Peripheral arterial disorder diagnosis in baseline	Baseline characteristic	Dichotomous variable equals 1 if there are ≥ 1 diagnoses for peripheral arterial disorder ICD-10 or disease codes during the baseline period.

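### The matched Cox models cluster the variance on matched pairs only, so their intervals can be too narrow if both anticoagulant choice and recorded event rates vary by hospital

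*SAP*

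**What the plan says.** SAP 4.1 describes the source: "The database provides claims data from 314 hospitals (as of June 2017) using the DPC system for medical service claims". SAP 10.1.1 matches 1:1, nearest neighbour within a caliper, on a propensity score. Its covariate list has no hospital term, and nothing requires both members of a pair to come from the same hospital.

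SAP 10.1.3 fits the matched Cox models "with robust sandwich estimates to account for the clustering within matched sets". Treatment is the only covariate unless a propensity-score component is unbalanced. The analysis tables in SAP 10.1.8 show only the index anticoagulant under covariates and strata.

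Hospital information is attached to each patient. SAP 8.4 defines hospital size as "Dichotomous variable equals 1 if hospital size on the index date is <500 beds and 0 if ≥ 500 beds", alongside physician specialty. Neither variable is in the propensity list of SAP 10.1.1. The limitations in Protocol 7.9 do not mention hospital. SAP 6.2 states: "All statistical tests will be performed at $p=0.05$ (two-sided) with no adjustment for multiplicity".

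**The concern.** The plan recognises that matched data may be dependent, but the only unit of dependence it allows for is the pair. Pairs formed without regard to hospital carry almost none of the correlation between patients of one hospital.

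Such correlation is plausible here. The endpoints in SAP 8.1 and 8.2 are read from disease-name fields in each hospital's claims, so coding and admission practice can shift recorded rates. Treatment is not randomised, so the mix of NOAC and warfarin can also differ by hospital. When both vary, their chance alignment adds variance to the log hazard ratio that a pair-clustered sandwich does not contain. The intervals are then too narrow and the unadjusted 0.05 tests reject too often.

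**Working it through.** **1. The plan's own figures.** SAP 6.2 tabulates "Required Sample Size per Group" for stroke/SE at 80% power and two-sided 0.05. Schoenfeld's formula gives total events = 4(1.960 + 0.842)² / ln(HR)². That is 120.3 for HR 0.6, 246.8 for HR 0.7 and 630.5 for HR 0.8. Dividing by the sum of the two event probabilities, p = 1 − exp(−rate × 2 years), gives N per group:
- HR 0.6, 1.2%/year: 120.3 / (0.02371 + 0.01430) = 3,166 (SAP 3,166)
- HR 0.7, 2.1%/year: 246.8 / (0.04113 + 0.02897) = 3,521 (SAP 3,488)
- HR 0.8, 2.6%/year: 630.5 / (0.05067 + 0.04075) = 6,898 (SAP 6,817)

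All 12 cells agree within about 1.2%. The table therefore assumes independent patients followed for two years, with a design effect of 1.

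**2. Inputs.** From the documents: 314 hospitals (SAP 4.1); a control rate of 2.1%/year (one row of SAP 6.2); previous-study counts of 14,830 warfarin, 16,176 apixaban and 4,438 edoxaban patients (Protocol 7.5), so at most 14,830 or 4,438 pairs; follow-up capped at "two years after the index date as primary and one year for a sensitive analysis". Assumed: HR 1; between-hospital SD of the NOAC-choice logit 1.0 (treatment ICC about 0.17); between-hospital SD s of the log event rate; hospital-size CV 0.8; 1 or 2 years at risk for every patient.

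**3. What s means.** ICC = p(exp(s²) − 1)/(1 − p). At two years p = 0.0411, so p/(1 − p) = 0.0429.
- s = 0.46: 0.0429 × 0.236 = 0.010. The 95% range of hospital rates is exp(2 × 1.96 × 0.46), about 6-fold.
- s = 0.88: 0.0429 × 1.169 = 0.050. The range is about 31-fold, which is extreme.

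**4. Closed form, equal hospitals.** Design effect = 1 + (m − 1) × ICC × 0.17, with m patients per hospital. False-positive rate = 2Φ(−1.96/√design effect).
- m = 29,660/314 = 94.5. ICC 0.01: 1 + 93.5 × 0.0017 = 1.16, giving 6.9%. ICC 0.05: 1.79, giving 14.3%.
- m = 8,876/314 = 28.3. ICC 0.01: 1.05, giving 5.5%. ICC 0.05: 1.23, giving 7.7%.

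The excess follows events per hospital: 29,660 × 0.0411/314 = 3.9 against 8,876 × 0.0411/314 = 1.2.

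**5. Simulation, 314 unequal hospitals, two years at risk, 1,500 replicates per cell.** A constant-hazard rate ratio stands in for the Cox model, and patient-level variance stands in for pair clustering.

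| Pairs | s | False positives, pair-only | Hospital-clustered |
|---|---|---|---|
| 14,830 | 0.46 | 8.1% | 5.8% |
| 14,830 | 0.63 | 10.6% | 4.9% |
| 14,830 | 0.88 | 19.1% | 5.5% |
| 4,438 | 0.46 | 5.3% | 4.7% |
| 4,438 | 0.63 | 7.3% | 5.5% |
| 4,438 | 0.88 | 9.8% | 5.5% |

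A repeat gave pair-only rates of 7.4%, 11.7% and 18.6% for 14,830 pairs, and 5.8%, 7.8% and 12.0% for 4,438. That is the spread to expect between runs.

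With one year at risk, pair-only rates were about 5% to 7% for s of 0.3 to 0.46. At s = 0.88 they were about 10% to 11% with 10,000 to 14,830 pairs (12.5% in another run at 14,830). With 4,438 pairs they were about 5% to 7%. Hospital-only and two-way clustering both held 4% to 6%.

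**6. Actual Cox sandwiches** (about 10,000 per arm before matching, 2.1%/year). The pair-clustered SE equalled the ordinary model SE to within about 0.1%. With s from 0.2 to 0.6 and choice-logit SD 0.7 or 1.2, the hospital-clustered SE was 1.01 to 1.13 times the pair-clustered SE, and coverage of the pair-only 95% interval ran from 95.2% down to 91.5%. With no hospital variation in treatment choice the SE ratio was 0.99 to 1.00.

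**The case against.** The strongest reply is that the effect may be negligible. Two years is a ceiling: follow-up also stops at discontinuation, switching or withdrawal, and the data end on 31 December 2017. The figure of 14,830 pairs is every warfarin patient in the previous study, and caliper matching can only reduce it. The highest error rates need a 31-fold spread of hospital event rates, which nothing in the documents supports. All of this stands, and it is why the likely effect on stroke/SE is modest.

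The count of 314 is for the whole database in June 2017; the number of hospitals contributing matched patients is not stated. A redacted block follows the Cox paragraph in SAP 10.1.3, so an undisclosed sensitivity analysis is possible. The visible specification is nevertheless clear, and no visible text handles hospital dependence.

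A reader might infer more than this:
- That the full cluster design effect applies, about 1.9 at ICC 0.01 with 94.5 patients per hospital. That would hold only if each hospital used a single drug. Treatment is chosen patient by patient, and the excess scales with how far choice differs between hospitals.
- That all four comparisons are affected, apixaban most. No dabigatran or rivaroxaban counts and no major-bleeding rate are given, so neither the ranking nor the certainty is supported.

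**Conclusion.** The point holds as a gap in the variance specification whose consequence is conditional. The pair-clustered sandwich gives no protection against hospital correlation. The intervals can be too narrow if both anticoagulant choice and recorded event rates vary by hospital, and are not if either is constant.

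For a stroke/SE-like rate of 2.1%/year and a choice-logit SD of 1.0, the false-positive rate is about 5% to 8% for a log-rate SD up to 0.46. It is about 10% to 18% at an extreme SD of 0.88 with 10,000 to 14,830 pairs and 1 to 2 years at risk. With 4,438 pairs it is about 5% to 9%, although one run reached 12% in the most extreme cell. Hospital variation and time at risk are assumptions, and the pair counts are upper limits or assumed.

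The error grows with events per hospital, but the four comparisons cannot be ranked. Nor does this point show that the hazard ratios are wrong. Confounding by hospital is a separate matter, left open because hospital size and physician specialty are not in the propensity score.

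**What to change.** In SAP 10.1.3, specify that the reported 95% intervals and p-values of the matched Cox models in 10.1.6 and 10.1.7 use a sandwich variance clustered on index hospital and on matched set: V = V_hospital + V_matched set − V_patient. Hospital-only clustering gives nearly the same result and is an acceptable simplification. Report the pair-only interval as a sensitivity result.

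The cost is a change to one SAP sentence, two extra variance runs and a simple combination per model, and an anonymised hospital identifier in the extract. I assume the identifier is available because hospital size is already attached to each patient. Intervals become somewhat wider if hospitals differ and barely move if they do not. Hazard ratios are unchanged, so this does not address confounding by hospital.

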10.1.4 Analysis of Continuous Data

Continuous data will be summarized using descriptive statistics, including the mean, standard deviation, median, first and third quartiles, and minimum and maximum. Baseline characteristics will be compared between patients treated with warfarin and patients treated with apixaban or

edoxaban using t-test or Mann-Whitney's U test depending on the distribution of the variables. In addition, standardized differences will be calculated for each variable.

10.1.5 Analysis of Categorical Data

Counts and percentages will be provided for dichotomous and polychotomous variables of baseline patient characteristics when performing descriptive analysis. Standardized differences will be calculated for each variable. For calculation of standardized differences, categorical variables will be converted into a set of binary indicators, one for each non-reference level of the variable and then a set of standardized differences defined⁶. In addition, the counts and percentages will be compared between patients treated with warfarin and patients treated with apixaban or edoxaban using chi-square tests.

10.1.6 Analyses of Efficacy/Effectiveness Endpoints

Propensity-Score-Matched Cohorts

For each propensity-score-matched cohort, a Cox proportional hazards model will be fit with the index OAC as a covariate. The hazard ratios with corresponding 95% confidence intervals and p-values will be reported. Kaplan-Meier estimates of time to the first event will be plotted. In addition, each endpoint will be summarized by the index OAC as described in the Section 8.1.

Matched cohorts by an IPTW method

For each matched cohort, a Cox proportional hazards model will be fit with the index OAC as a covariate. The hazard ratios with corresponding 95% confidence intervals and p-values will be reported. Kaplan-Meier estimates of time to first will be plotted. In addition, each endpoint will be summarized by the index OAC as described in the Section 8.1.

Pre-Matched Cohorts

Each endpoint will be summarized by the index OAC as described in the Section 8.1.

10.1.7 Analyses of Safety Endpoints

Propensity-Score-Matched Cohorts

For each propensity-score-matched cohort, a Cox proportional hazards model will be fit with the index OAC as a covariate. The hazard ratios with corresponding 95% confidence intervals and p-values will be reported for both any and major bleeding. Kaplan-Meier estimates of time to first

will be plotted. In addition, each endpoint will be summarized by the index OAC as described in the Section 8.2.

Matched cohorts by IPTW method

For each matched cohort, a Cox proportional hazards model will be fit with the index OAC as a covariate. The hazard ratios with corresponding 95% confidence intervals and p-values will be reported for both any and major bleeding. Kaplan-Meier estimates of time to first will be plotted. In addition, each endpoint will be summarized by the index OAC as described in the Section 8.2.

Pre-Matched Cohorts

Each endpoint will be summarized by the index OAC as described in the Section 8.2.

10.1.8 Summary of Analyses

Efficacy and safety analyses excluding descriptive summaries will be shown in the following table.

1) Propensity score matched cohorts

Outcome	Analysis Set	Supports Protocol Objective Number	Subgroups	Statistical Method	Covariates/Strata	Missing Data
Major bleeding	PS-matched patients ✓ Warfarin vs. apixaban Cohorts ✓ Warfarin vs. dabigatran Cohorts ✓ Warfarin vs. edoxaban Cohorts ✓ Warfarin vs. rivaroxaban Cohorts	safety, primary	NA	Cox proportional hazards model	Index OAC	No imputation
Major bleeding	PS-matched patients ✓ Warfarin vs. apixaban Cohorts ✓ Warfarin vs. dabigatran Cohorts ✓ Warfarin vs. edoxaban Cohorts ✓ Warfarin vs. rivaroxaban Cohorts	safety, primary	NA	Plot of Kaplan-Meier Estimates		No imputation
Major bleeding	PS-matched patients ✓ Warfarin vs. apixaban Cohorts ✓ Warfarin vs. dabigatran Cohorts ✓ Warfarin vs. edoxaban Cohorts ✓ Warfarin vs. rivaroxaban Cohorts	safety, primary	NA	Incidence rate (per 100 patient-year) (no statistical comparison)		No imputation
Any bleeding	PS-matched patients ✓ Warfarin vs. apixaban Cohorts ✓ Warfarin vs. dabigatran Cohorts	safety, primary	NA	Cox proportional hazards model	Index OAC	No imputation

Outcome	Analysis Set	Supports Protocol Objective Number	Subgroups	Statistical Method	Covariates/Strata	Missing Data
	✓ Warfarin vs. edoxaban Cohorts ✓ Warfarin vs. rivaroxaban Cohorts					
Any bleeding	PS-matched patients ✓ Warfarin vs. apixaban Cohorts ✓ Warfarin vs. dabigatran Cohorts ✓ Warfarin vs. edoxaban Cohorts ✓ Warfarin vs. rivaroxaban Cohorts	safety, primary	NA	Plot of Kaplan-Meier Estimates		No imputation
Any bleeding	PS-matched patients ✓ Warfarin vs. apixaban Cohorts ✓ Warfarin vs. dabigatran Cohorts ✓ Warfarin vs. edoxaban Cohorts ✓ Warfarin vs. rivaroxaban Cohorts	safety, primary	NA	Incidence rate (per 100 patient-year) (no statistical comparison)		No imputation
Major intracranial bleeding	PS-matched patients ✓ Warfarin vs. apixaban Cohorts ✓ Warfarin vs. dabigatran Cohorts ✓ Warfarin vs. edoxaban Cohorts ✓ Warfarin vs. rivaroxaban Cohorts	Safety Secondary	NA	Cox proportional hazards model	Index OAC	No imputation
Major intracranial bleeding	PS-matched patients ✓ Warfarin vs. apixaban Cohorts ✓ Warfarin vs. dabigatran Cohorts ✓ Warfarin vs. edoxaban Cohorts ✓ Warfarin vs. rivaroxaban	Safety Secondary	NA	Plot of Kaplan-Meier Estimates		No imputation

Outcome	Analysis Set	Supports Protocol Objective Number	Subgroups	Statistical Method	Covariates/Strata	Missing Data
	Cohorts					
Major intracranial bleeding	PS-matched patients ✓ Warfarin vs. apixaban Cohorts ✓ Warfarin vs. dabigatran Cohorts ✓ Warfarin vs. edoxaban Cohorts ✓ Warfarin vs. rivaroxaban Cohorts	Safety Secondary	NA	Incidence rate (per 100 patient-year) (no statistical comparison)		No imputation
Major GI bleeding	PS-matched patients ✓ Warfarin vs. apixaban Cohorts ✓ Warfarin vs. dabigatran Cohorts ✓ Warfarin vs. edoxaban Cohorts ✓ Warfarin vs. rivaroxaban Cohorts	Safety Secondary	NA	Cox proportional hazards model	Index OAC	No imputation
Major GI bleeding	PS-matched patients ✓ Warfarin vs. apixaban Cohorts ✓ Warfarin vs. dabigatran Cohorts ✓ Warfarin vs. edoxaban Cohorts ✓ Warfarin vs. rivaroxaban Cohorts	Safety Secondary	NA	Plot of Kaplan-Meier Estimates		No imputation
Major GI bleeding	PS-matched patients ✓ Warfarin vs. apixaban Cohorts ✓ Warfarin vs. dabigatran Cohorts ✓ Warfarin vs. edoxaban Cohorts ✓ Warfarin vs. rivaroxaban Cohorts	Safety Secondary	NA	Incidence rate (per 100 patient-year) (no statistical comparison)		No imputation
Any GI bleeding	PS-matched patients ✓ Warfarin vs. apixaban	Safety Secondary	NA	Cox proportional hazards model	Index OAC	No imputation

Outcome	Analysis Set	Supports Protocol Objective Number	Subgroups	Statistical Method	Covariates/Strata	Missing Data
	Cohorts ✓ Warfarin vs. dabigatran Cohorts ✓ Warfarin vs. edoxaban Cohorts ✓ Warfarin vs. rivaroxaban Cohorts					
Any GI bleeding	PS-matched patients ✓ Warfarin vs. apixaban Cohorts ✓ Warfarin vs. dabigatran Cohorts ✓ Warfarin vs. edoxaban Cohorts ✓ Warfarin vs. rivaroxaban Cohorts	Safety Secondary	NA	Plot of Kaplan-Meier Estimates		No imputation
Any GI bleeding	PS-matched patients ✓ Warfarin vs. apixaban Cohorts ✓ Warfarin vs. dabigatran Cohorts ✓ Warfarin vs. edoxaban Cohorts ✓ Warfarin vs. rivaroxaban Cohorts	Safety Secondary	NA	Incidence rate (per 100 patient-year) (no statistical comparison)		No imputation
Stroke/SE	PS-matched patients ✓ Warfarin vs. apixaban Cohorts ✓ Warfarin vs. dabigatran Cohorts ✓ Warfarin vs. edoxaban Cohorts ✓ Warfarin vs. rivaroxaban Cohorts	Effectiveness Primary	NA	Cox proportional hazards model	Index OAC	No imputation
Stroke/SE	PS-matched patients ✓ Warfarin vs. apixaban Cohorts ✓ Warfarin vs. dabigatran Cohorts	Effectiveness Primary	NA	Plot of Kaplan-Meier Estimates		No imputation

Outcome	Analysis Set	Supports Protocol Objective Number	Subgroups	Statistical Method	Covariates/Strata	Missing Data
	✓ Warfarin vs. edoxaban Cohorts ✓ Warfarin vs. rivaroxaban Cohorts					
Stroke/SE	PS-matched patients ✓ Warfarin vs. apixaban Cohorts ✓ Warfarin vs. dabigatran Cohorts ✓ Warfarin vs. edoxaban Cohorts ✓ Warfarin vs. rivaroxaban Cohorts	Effectiveness Primary	NA	Incidence rate (per 100 patient-year) (no statistical comparison)		No imputation

CCI

Outcome	Analysis Set	Supports Protocol Objective Number	Subgroups	Statistical Method	Covariates/Strata	Missing Data
CCI						

Outcome	Analysis Set	Supports Protocol Objective Number	Subgroups	Statistical Method	Covariates/Strata	Missing Data
CCI						

Outcome	Analysis Set	Supports Protocol Objective Number	Subgroups	Statistical Method	Covariates/Strata	Missing Data
CCI						

Outcome	Analysis Set	Supports Protocol Objective Number	Subgroups	Statistical Method	Covariates/Strata	Missing Data
CCI						

Outcome	Analysis Set	Supports Protocol Objective Number	Subgroups	Statistical Method	Covariates/Strata	Missing Data
CCI						

Outcome	Analysis Set	Supports Protocol Objective Number	Subgroups	Statistical Method	Covariates/Strata	Missing Data
CCI						

Outcome	Analysis Set	Supports Protocol Objective Number	Subgroups	Statistical Method	Covariates/Strata	Missing Data
CCI						

Outcome	Analysis Set	Supports Protocol Objective Number	Subgroups	Statistical Method	Covariates/Strata	Missing Data
CCI						

Outcome	Analysis Set	Supports Protocol Objective Number	Subgroups	Statistical Method	Covariates/Strata	Missing Data
CCI						

Outcome	Analysis Set	Supports Protocol Objective Number	Subgroups	Statistical Method	Covariates/Strata	Missing Data
CCI						

Outcome	Analysis Set	Supports Protocol Objective Number	Subgroups	Statistical Method	Covariates/Strata	Missing Data
CCI						

Outcome	Analysis Set	Supports Protocol Objective Number	Subgroups	Statistical Method	Covariates/Strata	Missing Data
CCI						

2) IPTW-matched cohorts

Outcome	Analysis Set	Supports Protocol Objective Number	Subgroups	Statistical Method	Covariates/Strata	Missing Data
Major bleeding	IPTW-matched patients ✓ Warfarin vs. apixaban Cohorts ✓ Warfarin vs. dabigatran Cohorts ✓ Warfarin vs. edoxaban Cohorts ✓ Warfarin vs. rivaroxaban Cohorts	safety, primary	NA	Cox proportional hazards model	Index OAC	No imputation
Major bleeding	IPTW-matched patients ✓ Warfarin vs. apixaban Cohorts ✓ Warfarin vs. dabigatran Cohorts ✓ Warfarin vs. edoxaban Cohorts ✓ Warfarin vs. rivaroxaban Cohorts	safety, primary	NA	Plot of Kaplan-Meier Estimates		No imputation
Major bleeding	IPTW-matched patients ✓ Warfarin vs. apixaban Cohorts ✓ Warfarin vs. dabigatran Cohorts ✓ Warfarin vs. edoxaban Cohorts ✓ Warfarin vs. rivaroxaban Cohorts	safety, primary	NA	Incidence rate (per 100 patient-year) (no statistical comparison)		No imputation
Any bleeding	IPTW-matched patients ✓ Warfarin vs. apixaban	safety, primary	NA	Cox proportional hazards model	Index OAC	No imputation

Outcome	Analysis Set	Supports Protocol Objective Number	Subgroups	Statistical Method	Covariates/Strata	Missing Data
	Cohorts ✓ Warfarin vs. dabigatran Cohorts ✓ Warfarin vs. edoxaban Cohorts ✓ Warfarin vs. rivaroxaban Cohorts					
Any bleeding	IPTW-matched patients ✓ Warfarin vs. apixaban Cohorts ✓ Warfarin vs. dabigatran Cohorts ✓ Warfarin vs. edoxaban Cohorts ✓ Warfarin vs. rivaroxaban Cohorts	safety, primary	NA	Plot of Kaplan-Meier Estimates		No imputation
Any bleeding	IPTW-matched patients ✓ Warfarin vs. apixaban Cohorts ✓ Warfarin vs. dabigatran Cohorts ✓ Warfarin vs. edoxaban Cohorts ✓ Warfarin vs. rivaroxaban Cohorts	safety, primary	NA	Incidence rate (per 100 patient-year) (no statistical comparison)		No imputation
Major intracranial bleeding	IPTW-matched patients ✓ Warfarin vs. apixaban Cohorts ✓ Warfarin vs. dabigatran Cohorts ✓ Warfarin vs. edoxaban Cohorts ✓ Warfarin vs. rivaroxaban Cohorts	Safety Secondary	NA	Cox proportional hazards model	Index OAC	No imputation
Major intracranial bleeding	IPTW-matched patients ✓ Warfarin vs. apixaban Cohorts ✓ Warfarin vs. dabigatran Cohorts	Safety Secondary	NA	Plot of Kaplan-Meier Estimates		No imputation

Outcome	Analysis Set	Supports Protocol Objective Number	Subgroups	Statistical Method	Covariates/Strata	Missing Data
	✓ Warfarin vs. edoxaban Cohorts ✓ Warfarin vs. rivaroxaban Cohorts					
Major intracranial bleeding	IPTW-matched patients ✓ Warfarin vs. apixaban Cohorts ✓ Warfarin vs. dabigatran Cohorts ✓ Warfarin vs. edoxaban Cohorts ✓ Warfarin vs. rivaroxaban Cohorts	Safety Secondary	NA	Incidence rate (per 100 patient-year) (no statistical comparison)		No imputation
Major GI bleeding	IPTW-matched patients ✓ Warfarin vs. apixaban Cohorts ✓ Warfarin vs. dabigatran Cohorts ✓ Warfarin vs. edoxaban Cohorts ✓ Warfarin vs. rivaroxaban Cohorts	Safety Secondary	NA	Cox proportional hazards model	Index OAC	No imputation
Major GI bleeding	IPTW-matched patients ✓ Warfarin vs. apixaban Cohorts ✓ Warfarin vs. dabigatran Cohorts ✓ Warfarin vs. edoxaban Cohorts ✓ Warfarin vs. rivaroxaban Cohorts	Safety Secondary	NA	Plot of Kaplan-Meier Estimates		No imputation
Major GI bleeding	IPTW-matched patients ✓ Warfarin vs. apixaban Cohorts ✓ Warfarin vs. dabigatran Cohorts ✓ Warfarin vs. edoxaban Cohorts ✓ Warfarin vs. rivaroxaban	Safety Secondary	NA	Incidence rate (per 100 patient-year) (no statistical comparison)		No imputation

Outcome	Analysis Set	Supports Protocol Objective Number	Subgroups	Statistical Method	Covariates/Strata	Missing Data
	Cohorts					
Any GI bleeding	IPTW-matched patients ✓ Warfarin vs. apixaban Cohorts ✓ Warfarin vs. dabigatran Cohorts ✓ Warfarin vs. edoxaban Cohorts ✓ Warfarin vs. rivaroxaban Cohorts	Safety Secondary	NA	Cox proportional hazards model	Index OAC	No imputation
Any GI bleeding	IPTW-matched patients ✓ Warfarin vs. apixaban Cohorts ✓ Warfarin vs. dabigatran Cohorts ✓ Warfarin vs. edoxaban Cohorts ✓ Warfarin vs. rivaroxaban Cohorts	Safety Secondary	NA	Plot of Kaplan-Meier Estimates		No imputation
Any GI bleeding	IPTW-matched patients ✓ Warfarin vs. apixaban Cohorts ✓ Warfarin vs. dabigatran Cohorts ✓ Warfarin vs. edoxaban Cohorts ✓ Warfarin vs. rivaroxaban Cohorts	Safety Secondary	NA	Incidence rate (per 100 patient-year) (no statistical comparison)		No imputation
Stroke/SE	IPTW-matched patients ✓ Warfarin vs. apixaban Cohorts ✓ Warfarin vs. dabigatran Cohorts ✓ Warfarin vs. edoxaban Cohorts ✓ Warfarin vs. rivaroxaban Cohorts	Effectiveness Primary	NA	Cox proportional hazards model	Index OAC	No imputation
Stroke/SE	IPTW-matched patients ✓ Warfarin vs. apixaban	Effectiveness Primary	NA	Plot of Kaplan-Meier Estimates		No imputation

Outcome	Analysis Set	Supports Protocol Objective Number	Subgroups	Statistical Method	Covariates/Strata	Missing Data
	Cohorts ✓ Warfarin vs. dabigatran Cohorts ✓ Warfarin vs. edoxaban Cohorts ✓ Warfarin vs. rivaroxaban Cohorts					
Stroke/SE	IPTW-matched patients ✓ Warfarin vs. apixaban Cohorts ✓ Warfarin vs. dabigatran Cohorts ✓ Warfarin vs. edoxaban Cohorts ✓ Warfarin vs. rivaroxaban Cohorts	Effectiveness Primary	NA	Incidence rate (per 100 patient-year) (no statistical comparison)		No imputation
CCI						

Outcome	Analysis Set	Supports Protocol Objective Number	Subgroups	Statistical Method	Covariates/Strata	Missing Data
CCI						

Outcome	Analysis Set	Supports Protocol Objective Number	Subgroups	Statistical Method	Covariates/Strata	Missing Data
CCI						

Outcome	Analysis Set	Supports Protocol Objective Number	Subgroups	Statistical Method	Covariates/Strata	Missing Data
CCI						

Outcome	Analysis Set	Supports Protocol Objective Number	Subgroups	Statistical Method	Covariates/Strata	Missing Data
CCI						

Outcome	Analysis Set	Supports Protocol Objective Number	Subgroups	Statistical Method	Covariates/Strata	Missing Data
CCI						

Outcome	Analysis Set	Supports Protocol Objective Number	Subgroups	Statistical Method	Covariates/Strata	Missing Data
CCI						

Outcome	Analysis Set	Supports Protocol Objective Number	Subgroups	Statistical Method	Covariates/Strata	Missing Data
CCI						

Outcome	Analysis Set	Supports Protocol Objective Number	Subgroups	Statistical Method	Covariates/Strata	Missing Data
CCI						

Outcome	Analysis Set	Supports Protocol Objective Number	Subgroups	Statistical Method	Covariates/Strata	Missing Data
CCI						

Outcome	Analysis Set	Supports Protocol Objective Number	Subgroups	Statistical Method	Covariates/Strata	Missing Data
CCI						

Outcome	Analysis Set	Supports Protocol Objective Number	Subgroups	Statistical Method	Covariates/Strata	Missing Data
CCI						

Outcome	Analysis Set	Supports Protocol Objective Number	Subgroups	Statistical Method	Covariates/Strata	Missing Data
CCI						

